
**Schedule of Tests and Procedures Table**

Item Time points	Screening period	Treatment period	Follow-up period
	Pre-procedure (-14d-0d)	Procedure details (0d)	From post-procedure to pre-discharge
Signing of ICF	▲		
Demographic data	▲		
Medical history	▲		
Vital signs 	▲	▲	▲
Pregnancy test 	▲		
Blood routine and blood biochemistry 	▲		▲
Myocardial enzyme spectrum 	▲		▲ (Within 48 hours post procedure)
ECG 	▲		▲ (Within 48 hours post procedure)
Inclusion/exclusion criteria	▲		
Center random		▲	
Clinical evaluation		▲	
Coronary angiography 		▲	
Coagulation functions 	▲		
Adverse cardiovascular event 		▲	▲
AE and SAE		▲	▲
Device defect		▲	
Cardiovascular concomitant medications	▲	▲	▲

**Notes:**

- (1) Vital signs: Systolic blood pressure, diastolic blood pressure and heart rate.
- (2) Pregnancy test: Only applicable to women of childbearing potential.
- (3) In order to protect the rights and interests of subjects, the examination results of blood routine and blood biochemistry within one month before procedure (the recent results shall prevail for those who have undergone examinations for many times) will be accepted: ① Blood routine: white blood cell count (WBC), red blood cell count (RBC), platelet count (PLT) and hemoglobin (HB); ② Renal function: serum creatinine (SCr); ③ Liver function: alanine aminotransferase (ALT) and aspartate aminotransferase (AST); ④ Blood lipids: triglyceride (TG), total cholesterol (TC), high density lipoprotein cholesterol (HDL-C) and low density lipoprotein cholesterol (LDL-C).
- (4) Myocardial enzyme spectrum: creatine kinase (CK), creatine kinase isoenzyme (CK-MB), cardiac troponin T (cTnT)/cardiac troponin I (cTnI) (choose one, not all are mandatory). Note: Post-procedure myocardial enzyme spectrum should be completed within 48 hours after procedure, and should be reexamined before discharge if the results are abnormal and clinically significant.
- (5) Post-procedure ECG should be done within 48 hours after procedure.
- (6) Coronary angiography is completed immediately after procedure and made into CD in each site.
- (7) Coagulation functions: Prothrombin time (PT), activated partial thromboplastin time (APTT), thrombin time (TT), fibrinogen (FIB). In order to protect the rights and interests of subjects, the examination results within one month before procedure will be accepted.
- (8) Adverse cardiovascular event includes major adverse cardiac events (MACE: including all-cause death, myocardial infarction [MI], and target lesion revascularisation [TLR]), target lesion failure (TLF, including cardiac death, target vessel myocardial infarction [TV-MI], and clinically indicated target lesion revascularisation [CI-TLR]), patient-oriented composite endpoint (PoCE, including all-cause death, all MIs, and all revascularisation events (target lesion revascularisation [TLR], target vessel non-target-lesion revascularisation [TVR] and non-target vessel revascularisation), etc.

## List of Abbreviations

Abbreviation	Complete spelling
%DS	percent diameter stenosis
ALT	Alanine Aminotransferase
AST	Aspartate Aminotransferase
APTT	Activated Partial Thromboplastin Time
CABG	coronary artery bypass grafting
CAD	coronary artery disease
CI-TLR	clinical indicated target lesion revascularisation
CK	creatinine kinase
CK-MB	creatinine kinase-myocardial band
cTnI	Cardiac troponin I
cTnT	Cardiac troponin T
FIB	Fibrinogen
HDL-C	High density lipoprotein cholesterol
ISR	in-stent restenosis
LDL-C	Low density lipoprotein cholesterol
MACE	major adverse cardiovascular events
MI	myocardial infarction
PCI	percutaneous coronary intervention
PoCE	patient-oriented composite endpoint
PT	prothrombin time
PTCA	percutaneous transluminal coronary angioplasty
RVD	reference vessel diameter
SCr	Serum creatinine
TC	Total cholesterol
TG	Triglyceride
TIMI	Thrombolysis In Myocardial Infarction
TLF	target lesion failure
TLR	target lesion revascularisation
TV-MI	target vessel myocardial infarction
TVR	target vessel revascularisation
TT	Thrombin Time

## **Text of Study Protocol**

### **1. Sponsor Information**

#### **1.1 Name of Sponsor**

Sino Medical Sciences Technology Inc.

### **2. Information on Study Sites and Principal Investigators**

The list of study sites and principal investigators (PIs) is present in Appendix 1.

During the clinical study, if the existing participating sites fail to obtain the approval of the clinical trial management department or the EC, resulting in the progress of the study significantly slower than the expected schedule, the sponsor should fully communicate and discuss with the coordinating investigator, and then make adjustments to the participating sites (abandonment or addition), and may file the list of clinical study sites in the Appendix without amending the text of the protocol. The final list of participating sites should be submitted to the clinical trial management departments and ECs of all participating sites for filling.

### **3. Background Information of Clinical Trial**

#### **3.1 R&D Background**

Since the success of the first percutaneous transluminal coronary angioplasty (PTCA) on September 16, 1977, with the continuous iteration and improvement of angioplasty techniques, PTCA has now become the most basic method of percutaneous coronary intervention (PCI), which is of great value for application to coronary artery disease (CAD).

The principle of PTCA is that the mechanical extrusion of vessel wall by balloon causes the atherosclerotic plaque to rupture irregularly, thus dilating the narrow lumen . However, some lesions, especially coronary artery calcification or dense fibrosis, are extremely difficult to be properly dilated with traditional balloons, which is often related to the failure of stent delivery or insufficient stent dilation. When the stent is placed at the poorly dilated lesions, it is very likely to lead to stent malapposition, incomplete expansion and poor symmetry, resulting

in a significant increase in periprocedural complications and an increase in risks of in-stent thrombosis and restenosis [2]. Because of the stent incomplete expansion, even post-dilation, the effect is also poor, thus leading to an increase in the incidence of adverse events such as in-stent thrombosis [3]. In recent years, some functional balloons, such as scoring balloons, have obviously improved the effect of complex coronary pre-dilation, greatly improving the acute procedural success rate and long-term prognosis.

Functional balloons are designed to combine their surface with a rigid metal or plastic element to enhance the interaction between the balloon surface and the plaque underneath. This improved interaction has two main advantages: the creation of a controlled plaque detachment that is not easily spread, and in addition, a reduction in longitudinal displacement or balloon slippage during dilation. Functional balloons currently on the market include cutting balloons with rigid microblades parallel to the longitudinal axis on the balloon surface, AngioSculpt balloons with Ni-Ti alloy wound along the balloon surface in a spiral shape on the longitudinal axis, and scoring balloons with nylon elements wound along the balloon surface parallel to the longitudinal axis. Compared with common balloons, functional balloons have shown certain advantages in the clinical application for the treatment of ISR, coronary ostial lesions, bifurcation lesions, small vessel lesions, and calcified lesions [4].

However, cutting balloons (such as Scoreflex) have a potential "relaxation" phenomenon in design and cannot produce multiple cutting effects [5]. At the same time, for cutting balloons, their inflexibility in clinical settings, difficulty in delivery, and poor passage at lesions (due to their high cross profile: 0.041–0.046 ") lead to a higher incidence of intra-procedural perforation [6]. It is particularly important to optimize the flexibility and other processes of existing functional balloons and reduce the risk of complications such as intra-procedural vessel perforation and damage to normal vessel walls, so as to benefit the large population of coronary artery disease, especially those PCI patients with calcified lesions.

A new generation of the scoring balloon catheter (Coronary Scoring Balloon Catheter) independently developed by Sino Medical Sciences Technology Inc. (hereinafter referred to as SINOMED) has undergone the type test at Tianjin Medical Devices Quality Supervision and Testing Center of the NMPA, and has been granted the test qualification report; meanwhile, Coronary Scoring Balloon Catheter has undergone the animal experimental study, verifying its safety. This study is intended to evaluate the safety and effectiveness of the new generation scoring balloon catheter (Coronary Scoring Balloon Catheter) developed and manufactured by SINOMED for human use, so as to provide the basis for its eventual formal marketing and application in China.

### **3.2 Basic Information of Product**

## (1) Product Characteristics

The Coronary Scoring Balloon Catheter has the following characteristics: (1) the scoring element made of Ni-Ti alloy with shape memory can restore its original shape, which is conducive to the safe withdrawal of the product from the blood vessel; (2) the spiral winding scoring element can act on the lesion at 360°, with a wide range of action; (3) the trapezoidal scoring similar to a triangle is conducive to the scoring element embedded in the plaque.

## (2) Structural Composition and Operating Principle

### 1) Device Composition

The balloon catheter consists of TIP, balloon protective sheath, balloon, scoring element, balloon inner tube, Marker, balloon outer tube, metal catheter, sleeve, connector, opening, and two markers of metal catheter. The product structure diagram is shown in Figure 1:

[figure not shown]

Figure 1 Structure diagram of Coronary Scoring Balloon Catheter

- 1) TIP
- 2) Balloon protective sheath
- 3) Balloon
- 4) Balloon inner tube
- 5) Marker [Two Markers are placed on the balloon inner tube (7), with their outer edges flush with the balloon neck]
- 6) Distal outer tube
- 7) Metal catheter (hypotube)
- 8) Sleeve
- 9) Connector
- 10) Opening (guidewire exit port)
- 11) Two markers of metal catheter
- 12) Proximal outer tube
- 13) Distal retainer
- 14) Scoring element

## 15) Proximal retainer

Note 1: D indicates the diameter of balloon post-dilation.

Note 2: L2 indicates the balloon effective length on the balloon catheter.

Note 3: L1 indicates the effective length of the balloon catheter.

Note 4: The complete Coronary Scoring Balloon Catheter is put into a protective sheath

The two developing points located on the balloon inner tube can accurately mark the position of the balloon under X-ray, which is helpful for checking the length of balloon dilated. The Ni-Ti alloy scoring element is spirally wound on the balloon, which is only attached to the balloon catheter at the distal and proximal ends, reducing the likelihood of slippage during balloon dilation. There are two markers (93 cm and 103 cm away from the distal end of the catheter, respectively) at the proximal end of the catheter, which are used to determine the position of the dilatation catheter relative to the front end of the guiding catheter in femoral artery puncture or brachial puncture. The guidewire exit port located at the front end of the catheter is about 24 cm away from the distal end. The Coronary Scoring Balloon Catheter can be used in combination with a guiding catheter with a minimum inner diameter of 1.68 mm (6Fr/0.066 inch); all the products can be used in combination with a guidewire with a maximum outer diameter of 0.36 mm (0.014 inch).

## 2) Operating Principle

The Coronary Scoring Balloon Catheter is a rapid exchange scoring balloon catheter. In interventional procedure, the Coronary Scoring Balloon Catheter is punctured percutaneously and travels along the blood vessel to the lesion site. The scoring element wound on the balloon in a spiral way can reduce the slippage of the balloon during dilation.

### 3.3 Intended Use and Related Information

#### (1) Intended Use (Indications, Intended Population, Application Site)

The Coronary Scoring Balloon Catheter is intended for the treatment of coronary artery stenosis, including in-stent restenosis (ISR) and complex type C lesions, to improve myocardial perfusion.

#### (2) Use Conditions and Method

This study product is intended for lesion localization and dilation under coronary angiography conditions and cannot be reused. The use method and steps of the product include pre-use inspection, unpacking, pre-procedure preparation, balloon catheter preparation, balloon catheter placement, balloon dilation process and balloon catheter withdrawal process. See the instructions for use (IFU) for details.

### **(3) Contraindications**

- All contraindications to angioplasty are contraindications to this product;
- Coronary artery spasm without organic stenosis;
- Left main lesion without bypass grafting or collateral circulation protection;
- Bifurcated lesions covered by stents;
- Stent fracture lesions;
- Patients with allergic reaction to the contrast agent;
- Patients with obvious abnormal coagulation function or hemorrhagic tendency;
- Patients who are contraindicated for antiplatelet or anticoagulant therapy;
- Other lesions that are not conducive to balloon dilation;
- Patients with severe infection or organ dysfunction;
- Patients who are not suitable for coronary artery bypass grafting (CABG);
- Except for the above matters, patients diagnosed by physicians as unsuitable for the use of relevant medical devices.

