## **5.2 Subject Enrollment**

### **5.2.1 Inclusion Criteria**

- (1) Patients are at least 18 to 75 years of age, male or not pregnant female;
- (2) Patients with asymptomatic ischemic evidence, stable or unstable angina pectoris or old myocardial infarction;
- (3) In situ or restenotic lesion(s) in coronary arteries, including in-stent restenosis (ISR);
- (4) Target lesion(s) must have a diameter of 2.0 mm ~ 3.5 mm and a length of  $\leq 30$  mm;
- (5) Target lesion(s) must have a percent diameter stenosis of  $\geq 70\%$  or  $\geq 50\%$  with evidence of ischemia;
- (6) Patients have a planned intervention at no more than two lesions, in different target vessels;
- (7) Investigators believe that target lesion atherosclerotic plaques require the scoring balloon treatment, in which the balloon can be passed through by pre-dilation.
- (8) Able to understand the purpose of the trial, voluntarily participate and sign the ICF.

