### **5.2.2 Exclusion Criteria**

- (1) Evidence of ongoing acute myocardial infarction within a week.
- (2) Chronic total occlusion (TIMI 0 pre-procedure), left main lesion, intervention-required three-vessel lesions, and bypass lesion.

- (3) Severe calcification and target lesion in a severe angulation ( $\geq 45$  degrees).
- (4) Patients with severe heart failure (NYHA Class III or above) or left ventricular ejection fraction  $<40\%$  (ultrasound or left ventricular angiography).
- (5) Patients with severe liver and renal dysfunction, as Cr  $>176.82$   $\mu\text{mol/L}$  or Cr  $>2.0$  mg/dl.
- (6) Patients with history of active digestive tract ulcer, history of cerebral hemorrhage or subarachnoid hemorrhage, history of ischemic stroke 6 months before procedure, as well as patients with bleeding tendency, antiplatelet preparation and anticoagulant therapy contraindications that cannot be treated with anticoagulant therapy.
- (7) Patients with allergies to heparin and contrast agent.
- (8) Target lesion demonstrating severe dissection prior to planned deployment of the study balloon.
- (9) Visible thrombus at the target lesion.
- (10) Patients to receive heart transplantation.
- (11) Patients who participated in other clinical trials of drugs or medical devices, but did not reach the primary endpoint.
- (12) Patients who are judged by the investigators to have poor compliance, are unable to complete the study as required, or are judged by the investigators to be unsuitable for participation in the study.
- (13) Patients who are not suitable for coronary artery bypass grafting (CABG).

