### 5.5.3 Norms for Using Device

Before using the test devices, the investigators should carefully read the relevant product IFU or materials and perform the procedures in strict accordance with IFU. (The following are recommended operations, and the operator may make slight modification according to the actual situations)

- The diameter, length, and number of balloons are selected, and the dilation pressure is determined by the operator according to the lesion condition.
- In use, the balloon should be dilated according to the nominal pressure specified in the IFU. A pressure monitoring device is recommended during the procedure to prevent excessive pressure.
- According to pre- and post-procedure conditions of the target lesion for the study balloon, pre-dilation of common balloon and stent implantation or post-dilation balloon can be selected for further treatment.
- Patients have a planned intervention at no more than two lesions, in different target vessels.
- When treated at the same time, the target and non-target lesions must be located in different vascular branches.
- If the target lesion and non-target lesion are treated at the same time, the target lesion can only be treated after the non-target lesion has been treated successfully.
- If a study balloon fails to dilate the target lesion, the operator will decide the follow-up treatment measures according to the lesion condition.
- In the event of a flow-limiting dissection or rupture during dilation, the operator will decide what treatment measures will be taken.

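### Three contraindications to the test device have no matching exclusion criterion, so a patient can meet every specific eligibility criterion and still be contraindicated for the device

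*Protocol*

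**What the plan says.** Section 3.3(3) of the protocol gives the contraindications for the investigational balloon. Four entries matter here: "Stent fracture lesions"; "Bifurcated lesions covered by stents"; "Patients with allergic reaction to the contrast agent"; and "Patients with severe infection or organ dysfunction".

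Section 5.2.1, inclusion (3), admits "In situ or restenotic lesion(s) in coronary arteries, including in-stent restenosis (ISR", with no carve-out for either of the two stent-related contraindications. In-stent restenosis is also part of the intended use in section 3.3(1).

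Section 5.2.2 has 13 exclusions, and the Protocol Abstract carries the same list. Exclusion (2) names the lesion types to be kept out: chronic total occlusion, left main, three-vessel disease needing intervention, and bypass lesions. Exclusion (5) begins "Patients with severe liver and renal dysfunction, as Cr" and continues with cut-offs of 176.82 µmol/L or 2.0 mg/dl. Exclusion (7) reads "Patients with allergies to heparin and contrast agent". Exclusion (12) lets the investigator keep out anyone judged unsuitable.

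Section 5.5.3 tells operators to read the IFU before using the devices and to "perform the procedures in strict accordance with IFU". The SAP does not restate the eligibility criteria.

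**The concern.** The contraindication list and the eligibility list sit in the same protocol and should agree. Where they do not, a site that follows the eligibility criteria exactly can randomise a patient to a device that the protocol says should not be used in that patient. Two of the three unmatched items concern previously stented segments, and in-stent restenosis is a group that inclusion (3) sets out to recruit.

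What is at stake is first patient safety. A second issue is how such a patient is handled afterwards. Section 5.6 relies on screening strictly against the inclusion and exclusion criteria, so a check against that list would not find these three conditions. If the patient is treated, no specific criterion has been breached, so nothing clearly makes the case a major violation for the per-protocol set in section 6.2. If the contraindication is noticed only after open-label allocation and the balloon is withheld, the subject may leave the analysis altogether.

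**Working it through.** No arithmetic decides this point. The check compares each relevant line of section 3.3(3) with every criterion in sections 5.2.1 and 5.2.2.

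| Contraindication, section 3.3(3) | Closest eligibility criterion | Result |
|---|---|---|
| Stent fracture | None. Exclusion (2) lists other lesion types; inclusion (3) takes in-stent restenosis unqualified | Gap |
| Bifurcation covered by a stent | None, for the same reason | Gap |
| Severe infection | None | Gap |
| Contrast allergy | Exclusion (7), heparin and contrast joined by *and* | Ambiguous |
| Severe organ dysfunction | Exclusion (5), liver and renal joined by *and*, creatinine cut-off only | Ambiguous |
| Left main lesion | Exclusion (2) | Matched |
| Haemorrhagic tendency | Exclusion (6) | Matched |
| Antiplatelet or anticoagulant contraindication | Exclusion (6) | Matched |
| Unsuitable for CABG | Exclusion (13), almost word for word | Matched |

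The last four rows show that the protocol's own practice is to turn contraindications into named exclusions. The three gaps are therefore better explained by incomplete carry-over than by a decision to leave all contraindications to the IFU.

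**The two ambiguous rows.** The ordinary reading of exclusion (7) is a list of two allergies, either of which excludes. Only a strictly conjunctive reading lets a patient with contrast allergy alone through. Exclusion (5) can likewise be read as two excluded conditions with a cut-off supplied for the renal one. On that reading severe liver dysfunction is excluded but has no stated threshold.

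**What happens if the balloon is withheld after allocation.**
1. The FAS (protocol section 6.2, SAP section 3) contains randomised subjects who received the study product.
2. Elimination criterion 6.3(2) removes subjects not treated with the test devices after inclusion.
3. Worst-observation imputation of the primary endpoint applies to patients in the FAS (SAP section 4). A subject outside the FAS would not be counted as a failure.
4. The subject could therefore drop out of the primary analysis.

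**Design figures.** The stated sample size reproduces: 7.85 × (2 × 0.96 × 0.04) / 0.10² = 60.3, rounded up to 61 per arm; 61 / 0.9 = 67.8, rounded up to 68 per arm and 136 in total. None of these figures depends on the mismatch.

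**The case against.** The strongest reply is that such patients would be kept out in practice:

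- Inclusion (7) requires the investigator to judge positively that the lesion needs scoring-balloon treatment.
- Angiography and the imaging criteria come before randomisation (Protocol Abstract, Study Method; SAP section 1.3), so lesion anatomy is seen before allocation.
- Section 3.3(4) warns operators to select patients carefully.
- Exclusion (12) is available for any patient judged unsuitable.
- Sections 10, 17.1 and 17.3 require training on the device and protocol, and familiarity with the indications. Section 3.3(3) is itself protocol text with which investigators must comply.

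All of this stands, and it means that exclusion (12) is not the only protection. But each safeguard is general or discretionary. None names the three conditions or creates a criterion that a monitor can check.

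A reader might also infer that the criteria plainly admit patients with contrast allergy alone, or with severe liver dysfunction and normal creatinine. The documents do not support that, because both exclusions have an ordinary reading that keeps such patients out.

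A further tempting inference is that withheld balloons would thin out difficult lesions in the test arm only and so favour non-inferiority. The documents do not show this. They give no contraindications for the control device. The abstract lists both products under test devices, so the IFU duty in section 5.5.3 can be read as covering both arms. Several of the contraindications concern the patient rather than the device. Nor can a size be attached: no frequency is given, and any assumed count of subjects would be set against an endpoint measured per lesion.

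**Conclusion.** The mismatch is real for three items: stent fracture, stent-covered bifurcation and severe infection. For these, a patient can meet every specific criterion and be randomised to a device that the protocol lists as contraindicated. Two other lines, exclusions (5) and (7), need clearer wording but do not contradict section 3.3(3).

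The conclusion rests only on comparing the two lists. It assumes nothing about how often these conditions occur, which the documents do not say, and it does not judge which clinical rule is right. The possible loss of a subject from the FAS after a late-recognised contraindication is a secondary, unquantified concern, and whether it would differ by arm cannot be shown. The point should be corrected for patient safety and for consistency of the protocol. It does not undermine the sample size or the non-inferiority test.

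**What to change.** Reconcile section 3.3(3), sections 5.2.1 and 5.2.2, and the copy in the Protocol Abstract line by line, so that no patient is eligible under one and contraindicated under another. The lines to settle are stent fracture, stent-covered bifurcation and severe infection. In the same revision, state whether exclusion (7) means either allergy or both, and whether exclusion (5) means either organ or both and how liver dysfunction is to be judged. The sponsor and investigators decide which wording stands.

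Have the reconciled list confirmed for every subject before the allocation is released. The inputs are already collected by then: history and laboratory tests at screening, and the angiogram that precedes randomisation. This also closes most of the route by which a balloon would be withheld after allocation.

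The cost is a wording amendment, which section 11.1 sends to the ethics committee, a few eligibility checkboxes and, depending on the wording chosen, possibly a few more screen failures. The SAP text on the endpoint, margin and sample size needs no change.
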